## 2. English title

Immunogenicity of an intradermal live attenuated tetravalent dengue vaccine among healthy volunteers:  
A pilot study

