## 5.3 Rationale

As in the setting of low- to middle-income countries, to demonstrating that lower doses of vaccine via intradermal route can still elicit robust immune responses, thereby lowering the overall cost of vaccination might be particularly meaningful ,with possible extra benefit of experiencing fewer side effects or risk of allergy. This study goal is to explores the potential of intradermal administration of Qdenga, hypothesizing that a lower dose via this route could achieve adequate immunogenicity compared to the standard subcutaneous administration, thus offering a cost-effective alternative particularly in low-resource settings where dengue is most prevalent.

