## 5.4 Objectives

### Primary Objectives

1. To evaluate the antibody response to dengue virus following administration of the second dose of QdengaTM via the intradermal route.
2. To evaluate the T-cell response (CD4 and CD8) to dengue virus following administration of the second dose of QdengaTM via the intradermal route.

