## 5.5 Literature review

Dengue fever, attributable to the dengue virus, represents a substantial global health concern. The advent of vaccines such as Qdenga and Dengvaxia has demonstrated potential in conferring immunity

against all four serotypes of the dengue virus. However, given the higher prevalence of dengue fever in resource-limited tropical regions, it is crucial to explore cost-reduction strategies. Intradermal injection, a previously successful dose-sparing technique, offers one such strategy. Nonetheless, the efficacy of intradermal administration for the newly developed Qdenga vaccine remains uncertain and warrants further investigation.

Study on the immunogenicity of the Qdenga vaccine, given subcutaneously, have shown promising results. One randomized, placebo-controlled Phase 2 study involving 148 participants aged 1.5 to 45 revealed seropositivity rates at month 36 of 97.3%, 98.7%, 88.0%, and 56.0% for DENV-1, -2, -3, and -4, respectively. Notably, seropositivity for DENV-4 varied significantly based on initial serostatus, with 89.5% in seropositive individuals compared to 21.6% in seronegative individuals. No vaccine-related serious adverse events (SAEs) were reported. The study demonstrated the persistence of neutralizing antibody titers and the Qdenga vaccine's tolerability over three years in both children and adults living in dengue-endemic regions.

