Another study evaluated the safety and immunogenicity of an early low-dose tetravalent dengue vaccine candidate (LD-TDV), which uses an attenuated serotype 2 backbone, administered intradermally either with an injector device (PharmaJet) or a needle-syringe in 67 subjects. The findings indicated that the intradermal administration of LD-TDV was well tolerated, with no significant safety concerns, and induced an immune response against all four dengue serotypes. The overall tetravalent seroconversion rates were 13.8% at Day 28 and 31.0% at Day 118, comparable to the previously reported 25% seroconversion rate for low-dose TDV given intradermally in 72 flavivirus-naive adults. Local reactions, such as induration (91.7% vs. 12.5%;  $P < .0001$ ) and pruritus (50% vs. 8.3%;  $P = .0034$ ), were more frequent following intradermal vaccination compared to subcutaneous administration. Most of these reactions were mild and resolved within one day.

This study aims to ensure the safety of vaccine recipients by comparing the administration of a second dose via the intradermal (ID) route after an initial subcutaneous (SC) dose with a control group receiving both doses subcutaneously (SC-SC). Previous research in Thailand on COVID-19 vaccines also evaluated the safety and immunogenicity of fractional (1/5th or 1/6th) doses of homologous ChAdOx1 or BNT162b2 administered intradermally following an initial intramuscular (IM) dose, demonstrating safety and immunogenicity. Based on this, the study hypothesizes that intradermal administration of fractional doses of the Qdenga vaccine after an initial SC dose will be immunogenic and have acceptable systemic adverse effects, with potential utility as a booster in the future.

The potential of intradermal vaccination to maintain or enhance immunogenicity while reducing the required dose has been highlighted in several reviews. This method could lower costs and improve vaccine accessibility in low-resource settings. However, further research is needed, as no randomized studies have yet evaluated both humoral and cell-mediated immune responses to intradermal Qdenga vaccination.

[figure not shown]

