## 5.6 Conceptual framework

A new dengue vaccine, Qdenga™, has recently become available in Thailand. As a live-attenuated vaccine, it does not require pre-vaccination serological screening for dengue immunity, unlike Dengvaxia™. However, access to Qdenga™ remains limited due to its high cost and the fact that it is not yet reimbursable for the general population. The vaccine is designed for subcutaneous administration and is given as a two-dose series, with the second dose administered three months after the first.

In theory, intradermal administration may elicit comparable immune responses while using a lower vaccine dose, owing to the high density of antigen-presenting cells in the dermal layer. Based on this rationale, investigators from multiple departments within the Faculty of Medicine have initiated a collaborative study to evaluate the immunogenicity and safety of intradermal Qdenga™ administration in healthy volunteers. Immune responses will be assessed at baseline, 30 days after the first dose, and 30 days after the second dose. All participants will receive the first dose subcutaneously as per standard practice, then be randomized to receive the second dose either subcutaneously or intradermally.

This study aims to enhance understanding of the immune response elicited by Qdenga™ given via different administration routes and to generate data that may inform future vaccine implementation strategies and potential dose-sparing approaches.

CONSORT FLOW Diagram

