### 5.7.3 Study samples

#### 5.7.3.1 Inclusion Criteria

1. Thai adult aged 18-60 years with positive dengue IgG from screening test, who not previously received dengue vaccine.
2. The subjects are able to and willing to comply with the requirements of the clinical trial program and could complete the 3-month follow-up of the study.
3. Individuals who are in good health condition at the time of entry into the trial as determined by medical history, physical examination and clinical judgment of the investigator and meet the requirements of immunization
4. The subject can provide with informed consent and sign informed consent form

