## Study flow

## Study procedure

Study period	Screening	Treatment	Treatment	Follow up	
		Vaccine dose 1	Vaccine dose 2	Day 30 ± 3 day	Day 120 ± 3 days
Day/week	Day 0 to -7	Day 0	Day 90 ± 3 days	Day 30 ± 3 day	Day 120 ± 3 days
Informed consent, medical history	X				
Contraceptive counselling	X				
Screen dengue IgG	X				
Review of Inclusion/exclusion criteria		X	X		
Physical examination		X	X		
Body Weight/ Height/ Vital sign		X	X		
Concomitant medication check		X	X		

Blood collection*		X	X		X
Randomization		X			
Vaccination		X	X		
Adverse event check (also by google form+/- telephone at 7, 30 day after each vaccination)		X		X	X

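### The antibody analysis compares levels in people who are all dengue-IgG-positive at entry and all primed subcutaneously, so it does not isolate the response to the second dose

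*Combined protocol and SAP*

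**What the plan says.** **Population.** Section 5.7.3.1 (Inclusion Criteria) admits a "Thai adult aged 18-60 years with positive dengue IgG from screening test, who not previously received dengue vaccine". The Study procedure table has a matching screening entry, "Screen dengue IgG". The title is wider: "Immunogenicity of an intradermal live attenuated tetravalent dengue vaccine among healthy volunteers". The primary objectives name no population, and section 5.3 gives the hypothesis without a serostatus limit: "hypothesizing that a lower dose via this route could achieve adequate immunogenicity compared to the standard subcutaneous administration". No section explains the IgG restriction or limits inference to seropositive adults.

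**Treatment.** Sections 5.6 and Arms and Interventions give all participants the first dose subcutaneously. The arms differ only in the route of dose 2.

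**Objective.** Primary objective 1 begins "To evaluate the antibody response to dengue virus following administration of the second dose of Qdenga" and specifies the intradermal route.

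**Variable and analysis.** Section 5.7.8 lists the antibody variable as the ELISA level at days 0, 30 and 120. Under Antibody analysis in section 5.7.9, the assay captures a mixture of the four serotypes and detects human IgG. Section 5.7.12 compares quantitative variables by t-test or Wilcoxon rank-sum test at P < 0.05. It names no change score, no baseline covariate and no definition of a response.

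**The concern.** The objective asks what dose 2 does, but the listed variable is how much antibody is present. These differ in this trial because nobody starts from zero. Each participant enters with dengue IgG, the same kind of marker that the ELISA measures, and then has a full first dose before the arms diverge.

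If Day 120 levels look alike in the two arms, one explanation is that the intradermal dose worked as well as the subcutaneous one. Another is that antibody from infection and dose 1 dominates both arms and dose 2 added little in either, or little in the intradermal arm. The planned comparison cannot tell these apart. Sections 5.3 and 5.6 look ahead to adequate immunogenicity and dose sparing, so the distinction decides what the pilot can pass on to a later trial.

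**Working it through.** **1. Sample size.** Section 5.7.6 gives two groups of 12: 2 × 12 = 24, which agrees. It gives no effect size, SD, margin or power, so nothing further can be reproduced.

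**2. What a Day 120 level contains.** On the log scale write Day 120 level = P + R, where P is the level just before dose 2 and R is the response to dose 2. The difference in arm means is then

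(P_ID − P_SC) + (R_ID − R_SC).

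Randomisation makes the first bracket zero on average. But R_ID, which objective 1 asks for, cannot be recovered from Day 120 levels alone: R_ID = R_SC = 0 and R_ID = R_SC = any large value give the same expected difference. Change from Day 0 does not solve this, because it adds the dose 1 response to R.

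**3. How different the arms could be and still look similar.** Inputs: 12 per arm (section 5.7.6) and a two-sided 5% level (section 5.7.12 gives 0.05; two-sided is my assumption).
- 95% half-width for a difference in means = t(0.975, 22) × √(2/12) × SD = 2.074 × 0.408 × SD = 0.85 SD.
- Difference detectable with 80% power by t-test at 12 per arm: 1.20 SD.

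SD here is the between-person SD of Day 120 log level, which includes the spread from past infection and dose 1. The documents give no value for it.

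**4. What the pre-dose-2 value could buy.** Let ρ be the within-person correlation of log level before dose 2 and at Day 120. The documents do not give ρ, so a range is assumed, with equal SDs at the two times. The multiplier on 0.85 SD is √(1 − ρ²) for adjustment (ignoring the degree of freedom spent) and √(2(1 − ρ)) for change.

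| Assumed ρ | Level alone | Change | Adjusted level |
|---|---|---|---|
| 0.5 | 0.85 SD | 0.85 × 1.000 = 0.85 SD | 0.85 × 0.866 = 0.73 SD |
| 0.7 | 0.85 SD | 0.85 × 0.775 = 0.66 SD | 0.85 × 0.714 = 0.60 SD |
| 0.9 | 0.85 SD | 0.85 × 0.447 = 0.38 SD | 0.85 × 0.436 = 0.37 SD |

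(Products use the unrounded 0.8467.)

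**5. Is a pre-dose-2 sample planned?** The sections disagree:

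| Place | Day 0 | Day 30 | Before dose 2 (Day 90) | 30 days after dose 2 (Day 120) |
|---|---|---|---|---|
| 5.6 Conceptual framework | yes | yes | not listed | yes |
| 5.7.8 Study variables | yes | yes | not listed | yes |
| 5.7.9 Blood collection | not listed | not listed | yes | yes |
| Study procedure table | yes | no | yes | yes |

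If only Day 30 exists, change from Day 30 to Day 120 mixes the dose 2 response with 60 days (90 − 30) of possible decline after dose 1.

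**6. Serostatus.** Section 5.5 reports month-36 DENV-4 seropositivity after subcutaneous vaccination "with 89.5% in seropositive individuals compared to 21.6% in seronegative individuals": 89.5 − 21.6 = 67.9 points. The figures are consistent with the overall 56.0%: 34/38 = 89.5%, 8/37 = 21.6% and (34 + 8)/75 = 56.0%.

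**The case against.** **Randomisation already isolates the route.** This is the strongest argument, and it stands for the contrast: mean Day 120 level is an unbiased comparison of the two second-dose routes. It does not supply the response in the intradermal arm, which is how objective 1 is worded, and at ±0.85 SD a null difference says little.

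**Change score or adjustment is a matter of preference.** That also stands, and either is acceptable. Using neither is the problem.

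**The population wording is not false.** Healthy volunteers agrees with the inclusion criterion on good health, objectives normally take their population from eligibility, and the objectives already specify the second dose. On its own the missing serostatus is a labelling and generalisability point. It matters here because it affects how the antibody level can be read.

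**Stronger readings that the documents do not support:**
- A reader might infer that the hypothesis rests on flavivirus-naive data, given text such as "comparable to the previously reported 25% seroconversion rate for low-dose TDV given intradermally in 72 flavivirus-naive adults" and the 96 flavivirus-naive adults in section 5.5. But section 5.5 derives the hypothesis from fractional intradermal COVID-19 vaccine data. The naive dengue studies are background, and the 67-subject study has no stated serostatus.
- A reader might infer that the trial states a conclusion about people whom it excludes. It is a pilot plan with no conclusion, and section 5.6 says only that its data may inform later strategies.
- The remark in section 5.6 that "it does not require pre-vaccination serological screening for dengue immunity" describes the product. It makes no claim about who is studied.
- The 67.9-point gap might be taken as the size of the error. It is one serotype at month 36 after subcutaneous vaccination; this trial uses a pooled ELISA at Day 120. Vaccine viremia (16% against 49%) is not a listed outcome either.

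**Conclusion.** The concern holds as a gap between objective 1 and its analysis. With everyone IgG-positive at entry and primed subcutaneously, Day 120 level or positivity alone cannot show a response to dose 2, and the plan names no use of the earlier value. The size is expressible only in SD units: at 12 per arm, equal observed Day 120 means remain compatible with a difference of about 0.85 SD in either direction. Adjustment narrows this to between 0.73 and 0.37 SD for assumed correlations of 0.5 to 0.9; the change score gains nothing at 0.5.

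This rests on roughly normal log levels, two-sided testing and all 24 participants contributing. Even the within-person rise is not purely dose 2, since no arm goes without a second dose and decline or natural exposure over the 30 days is included. The Study procedure table places randomisation at Day 0, but both arms receive the same first dose, so the pre-dose-2 value is still unaffected by route.

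No sample-size or alpha figure changes. The serostatus figures show that serostatus matters and that inference should stop at IgG-positive adults; they show no more than that.

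**What to change.** 1. **Reconcile the sampling days first.** Sections 5.6, 5.7.8, 5.7.9 and the Study procedure table must agree on which draws are taken. The analysis below needs the draw before dose 2 to be among them.
2. **Define the response.** In sections 5.7.8 and 5.7.12, define the antibody response to dose 2 as the within-person log fold-rise from the pre-dose-2 sample to Day 120. Report it for each arm with a 95% confidence interval.
3. **Compare arms** on that rise, or on log Day 120 level adjusted for the pre-dose-2 value. Choose one in advance.
4. **Limit the interpretation.** State that post-vaccination level or positivity alone will not be treated as evidence of immunogenicity.
5. **Name the population.** Say in the objectives and hypothesis that participants are dengue-IgG-positive adults, give the reason for the restriction, and state that inference does not extend to seronegative people.

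**Cost.** Eligibility and sample size are unchanged. If the pre-dose-2 draw in section 5.7.9 and the Study procedure table is confirmed, no extra sample is needed; if it is not, one draw has to be added. The rest is wording, slightly more analysis work and a narrower claim.

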#### 5.7.3.2 Exclusion criteria

1. Have a medical history or family history of convulsion, epilepsy, encephalopathy and psychosis.
2. Be allergic to any component of the research vaccines or used to have a history of hypersensitivity or serious reactions to vaccination.
3. Women with positive urine pregnancy test, pregnant or breast-feeding, or have a pregnancy plan within six months.
4. Have acute infectious diseases, including dengue infection
5. Have severe chronic diseases or condition in progress cannot be controlled.  
For example, poor controlled DM and uncontrolled HT.
6. Have the history of urticaria 1 year before receiving the investigational vaccine.
7. Have needle sickness.

8. Have the history of immunosuppressive therapy, cytotoxic therapy or systemic corticosteroids
9. Have received blood products within 6 months before injection of investigational vaccines.
10. Not be able to follow the protocol or not be able to understand the informed consent according to the researcher's judgment, due to various medical, psychological, social or other conditions.
11. Recent administration within 1 months or planned to get any live attenuated vaccine within the study period.

#### **5.7.4 Subject withdrawal criteria**

1. The participant chooses to withdraw from the study at any time.
2. The study is discontinued at the discretion of the investigator if continuation poses a potential risk to the participant.
3. The participant wishes to receive other vaccines (e.g., pneumococcal vaccine, zoster vaccine) within 30 days after receiving the study vaccine.
4. The participant develops anaphylaxis or any severe adverse event following the first dose of the vaccine.

#### **5.7.5 Study termination criteria**

1. The study procedures conflict with national or governmental policies.
2. New scientific evidence emerges, indicating that continuation of the study provides no meaningful benefit.
3. Intradermal vaccination results in severe local adverse events—such as abscess, granulomatous reactions, or skin necrosis—in more than 10% of study participants.

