#### **5.7.6 Sample size calculation**

In this study, a total sample size of 24 participants will be used, allocated equally into two groups of 12 participants each. Based on the recommendation by Julious, a sample size of 12 subjects per group is considered adequate to achieve reasonable precision for preliminary estimates in a pilot study.

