### Arms and Interventions:

Arm 1: subcutaneous Qdenga for 1st vaccination then intradermal Qdenga for 2nd vaccination

Arm 2: subcutaneous Qdenga for 1st vaccination then subcutaneous Qdenga for 2nd vaccination

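### The 10% stopping limit for intradermal harm is set over all study participants, half of whom cannot have the event, so read literally it acts only at 25% of those exposed

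*Combined protocol and SAP*

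**What the plan says.** Section 5.7.5 lists three termination criteria. Only the third carries a number. Its subject is harm from one route, "Intradermal vaccination results in severe local adverse events", with abscess, granulomatous reaction and skin necrosis as examples, and its limit is reached when these occur "in more than 10% of study participants".

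Section 5.7.6 plans 24 participants, "allocated equally into two groups of 12 participants each". Section 5.6 says that "All participants will receive the first dose subcutaneously as per standard practice", and that they will "then be randomized to receive the second dose either subcutaneously or intradermally". The arms listed under Arms and Interventions agree: Arm 1 has the ID second dose, and Arm 2 has both doses subcutaneously.

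The protocol does not define study participants for this rule, does not restrict the percentage to ID recipients, and gives no event count. The nearest other provision is item 2 of section 5.7.4: "The study is discontinued at the discretion of the investigator if continuation poses a potential risk to the participant".

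**The concern.** The event in criterion 3 can occur only after an ID injection, but the percentage is taken over a group that, on its plain wording, includes the subcutaneous arm. Twelve people who are not at risk then dilute the rate by half. A limit that reads as 10% tolerates 16.7% among those exposed and acts at 25%.

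The other reading, a percentage of those who received the ID dose, is at least as natural given the subject of the sentence. So two people applying the same rule to the same data could decide differently. This matters because it is the only numeric safety limit in the plan, it guards the arm on the non-standard route, and safety and reactogenicity of ID administration is the secondary objective.

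**Working it through.** **Inputs.** Limit: strictly more than 10% (5.7.5). Planned total 24, with 12 per group (5.7.6). Exposed to ID: one group of 12, at dose 2 only (5.6; Arms and Interventions). Drop-out and the true rate of severe local ID reactions are not given.

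**The plan's own figure.** 2 × 12 = 24 reproduces. The rule states no event count, so there is none to reproduce.

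**Trigger.** The rule acts at the smallest whole number r with r/n > 0.10, that is, the integer part of 0.10 × n, plus 1.

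- n = 24: 0.10 × 24 = 2.4, so r = 3. Two are 2/24 = 8.3% (continue); three are 3/24 = 12.5% (stop). Three are 3/12 = 25% of those exposed.
- n = 12: 0.10 × 12 = 1.2, so r = 2. One is 1/12 = 8.3% (continue); two are 2/12 = 16.7% (stop).

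The readings conflict at exactly two affected participants and nowhere else.

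**Drop-out.** With 20 to 24 participants counted, two are at most 2/20 = 10.0%, which does not exceed the limit; at 19 they do (10.5%). With 10 to 12 ID recipients, one is at most 1/10 = 10.0%, which does not exceed it; at 9 it does (11.1%). So moderate drop-out does not remove the conflict.

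**Chance of each outcome.** Only the 12 ID recipients can have the event, so the number affected is taken as binomial(12, p), counted once all 12 have been dosed and followed. The values of p are assumptions.

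| Assumed true ID rate p | Acts at 3 (24 counted): P(≥3) | Acts at 2 (12 counted): P(≥2) | Readings conflict: P(exactly 2) |
|---|---|---|---|
| 2% | 0.2% | 2.3% | 2.2% |
| 5% | 2.0% | 11.8% | 9.9% |
| 10% | 11.1% | 34.1% | 23.0% |
| 20% | 44.2% | 72.5% | 28.3% |

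Worked line for p = 5%: P(exactly 2) = 66 × 0.05² × 0.95¹⁰ = 0.099; P(≥2) = 1 − 0.95¹² − 12 × 0.05 × 0.95¹¹ = 0.118; the difference, P(≥3), is 0.020.

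The chance of stopping reaches 50% at a true rate of 21.7% when three are needed and 13.6% when two are needed.

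**Running denominator.** The rule does not say whether the percentage is of planned participants or of those dosed so far. On a running ID denominator, one case among the first 9 is 1/9 = 11.1% and would already stop the study. The chance of at least one among the first 9 is 1 − 0.95⁹ = 37% at p = 5% and 1 − 0.90⁹ = 61% at p = 10%. Changing the denominator alone is therefore not enough; the count must be stated.

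**The case against.** The strongest case against acting has four parts.

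- *An investigator would apply the rule to ID recipients anyway.* Quite possibly, and then it acts at two. But the wording points to everyone in the study and nothing else in the protocol corrects it. A stopping rule should not depend on the reader.
- *The investigator can stop regardless.* Item 2 of section 5.7.4 gives that discretion. It sits under subject withdrawal and does not set this limit, but it is a real backstop. A reader might infer that two cases of abscess or necrosis would go unanswered; the protocol does not support that.
- *Stopping would change little.* This largely stands. The ID injection is the second and last dose; afterwards only the Day 120 visit and adverse event checks remain. Each second dose falls at Day 90 ± 3 days, so how ID doses are spread depends on the pace of enrolment, which the protocol does not describe, and no staggering is planned. A reader might infer that the literal wording exposes more people to harm. That cannot be shown: if all 12 are dosed before the events are known, nobody is spared under either reading.
- *The conflict is unlikely.* Section 5.5 reports that an early low-dose candidate given intradermally was well tolerated, and that local reactions, though more frequent by this route, were mostly mild and brief. This gives no severe-event rate for the present product and dose, but it makes the 2% and 5% rows the fairer guide, rather than 10% or 20%.

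Choosing two rather than three is also partly a matter of risk tolerance, and that choice belongs to the sponsor.

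**Conclusion.** The point holds. As written, the limit is set over a denominator of which half cannot have the event, so a literal reader continues at 2 of 12 exposed and stops only at 3 of 12. The trigger counts of 3 and 2 are exact for the planned numbers.

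The practical size is modest. At assumed true rates of 2% to 5%, the readings conflict with a chance of about 2% to 10%, and any protection reaches only participants still awaiting the ID dose. No saving of ID doses is claimed. Nor do the documents show that the sponsor means to tolerate 25% among those exposed; the wording may simply not have been checked against the group sizes. The immunogenicity objectives and their analysis are not affected. It should still be corrected, because it is the plan's only numeric safety limit and the correction is small.

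**What to change.** In criterion 3 of section 5.7.5, make ID recipients the denominator and let a count decide. For example: *in 2 or more participants who received the intradermal dose (more than 10% of the 12 planned)*. Add that the count governs whatever number has been dosed, so that a single early case does not trigger a running percentage, and so that percentage and count cannot conflict if 9 or fewer receive the ID dose.

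If the sponsor prefers three, write *3 or more of the 12 ID recipients (at least 25%)*. More than 25% would be wrong: 3/12 is exactly 25%, so the trigger would move to four.

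The cost is one line of text, with no new data or visits. The downside of two rather than three is a greater chance of stopping when the true rate is low: 12% against 2% at an assumed 5%, and 34% against 11% at 10%.
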